**Table 2 Adverse Event Severity Grading Scale**

Severity	Description
Mild	Discomfort noticed, but no disruption of normal daily activity
Moderate	Discomfort sufficient to reduce or affect normal daily activity
Severe	Incapacitating with inability to work or to perform normal daily activity

Note: Regardless of severity, some events may also meet seriousness criteria. Refer to definition of a serious adverse event (see Section 5.1.2).

### **5.3.4 Assessment of Causality of Adverse Events**

Investigators should use their knowledge of the healthy volunteer, the circumstances surrounding the event, and an evaluation of any potential alternative causes to determine whether or not an adverse event is considered to be related to the study drug, indicating "yes" or "no" accordingly. The following guidance should be taken into consideration:

- Temporal relationship of event onset to the initiation of study drug.
- Course of the event, considering especially the effects of dose reduction, discontinuation of study drug.
- Known association of the event with the study drug or with similar treatments.
- Known association of the event with the disease under study.
- Presence of risk factors in the healthy volunteer or use of concomitant medications known to increase the occurrence of the event.
- Presence of non-treatment-related factors that are known to be associated with the occurrence of the event.

### **5.3.5 Procedures for Recording Adverse Events**

Investigators should use correct medical terminology/concepts when recording adverse events on the Adverse Event eCRF. Avoid colloquialisms and abbreviations.

Only one adverse event term should be recorded in the event field on the Adverse Event eCRF.

#### **5.3.5.1 Diagnosis versus Signs and Symptoms**

A diagnosis (if known) should be recorded on the Adverse Event eCRF rather than individual signs and symptoms (e.g., record only liver failure or hepatitis rather than jaundice, asterixis, and elevated transaminases). However, if a constellation of signs and/or symptoms cannot be medically characterized as a single diagnosis or syndrome at the time of reporting, each individual event should be recorded on the Adverse Event eCRF. If a diagnosis is subsequently established, all previously reported adverse events based on signs and symptoms should be nullified and replaced by one adverse event report based on the single diagnosis, with a starting date that corresponds to the starting date of the first symptom of the eventual diagnosis.

### **5.3.5.2 Adverse Events Occurring Secondary to Other Events**

In general, adverse events occurring secondary to other events (e.g., cascade events or clinical sequelae) should be identified by their primary cause, with the exception of severe or serious secondary events. However, medically significant adverse events occurring secondary to an initiating event that are separated in time should be recorded as independent events on the Adverse Event eCRF. For example:

- If vomiting results in mild dehydration with no additional treatment in a healthy adult, only vomiting should be reported on the eCRF.
- If vomiting results in severe dehydration, both events should be reported separately on the eCRF.
- If a severe GI hemorrhage leads to renal failure, both events should be reported separately on the eCRF.
- If dizziness leads to a fall and subsequent fracture, all three events should be reported separately on the eCRF.

All adverse events should be recorded separately on the Adverse Event eCRF if it is unclear as to whether the events are associated.

### **5.3.5.3 Persistent or Recurrent Adverse Events**

A persistent adverse event is one that extends continuously, without resolution, between healthy volunteer evaluation time-points. Such events should only be recorded once on the Adverse Event eCRF. The initial severity of the event should be recorded, and the severity should be updated to reflect the most extreme severity any time the event worsens. If the event becomes serious, the Adverse Event eCRF should be updated to reflect this.

A recurrent adverse event is one that resolves between subject evaluation time-points and subsequently recurs. Each recurrence of an adverse event should be recorded separately on the Adverse Event eCRF.

### **5.3.5.4 Abnormal Laboratory Values**

Not every laboratory abnormality qualifies as an adverse event. A laboratory test result should be reported as an adverse event if it meets any of the following criteria:

- Accompanied by clinical symptoms.
- Results in a change in study treatment (e.g., dosage modification, treatment interruption, or treatment discontinuation).
- Results in a medical intervention (e.g., potassium supplementation for hypokalemia) or a change in concomitant therapy.
- Clinically significant in the Investigator's judgment.

It is the Investigator's responsibility to review all laboratory findings. Medical and scientific judgment should be exercised in deciding whether an isolated laboratory abnormality should be classified as an adverse event.

If a clinically significant laboratory abnormality is a sign of a disease or syndrome (e.g., alkaline phosphatase and bilirubin 5 times ULN associated with cholecystitis), only the diagnosis (i.e., cholecystitis) should be recorded on the Adverse Event eCRF.

If a clinically significant laboratory abnormality is not a sign of a disease or syndrome, the abnormality itself should be recorded on the Adverse Event eCRF, along with a descriptor indicating if the test result is above or below the normal range (e.g., "elevated potassium", as opposed to "abnormal potassium"). If the laboratory abnormality can be characterized by a precise clinical term per standard definitions, the clinical term should be recorded as the adverse event. For example, an elevated serum potassium level of 7.0 mEq/L should be recorded as "hyperkalemia".

Observations of the same clinically significant laboratory abnormality from visit to visit should not be repeatedly recorded on the Adverse Event eCRF, unless the etiology changes. The initial severity of the event should be recorded, and the severity or seriousness should be updated any time the event worsens.

### **5.3.5.5      Abnormal Vital Sign Values**

Not every vital sign abnormality qualifies as an adverse event. A vital sign result should be reported as an adverse event if it meets any of the following criteria:

- Accompanied by clinical symptoms.
- Results in a change in study treatment (e.g., dosage modification, treatment interruption, or treatment discontinuation).
- Results in a medical intervention or a change in concomitant therapy.
- Clinically significant in the Investigator's judgment.

It is the Investigator's responsibility to review all vital sign findings. Medical and scientific judgment should be exercised in deciding whether an isolated vital sign abnormality should be classified as an adverse event.

If a clinically significant vital sign abnormality is a sign of a disease or syndrome (e.g., high BP), only the diagnosis (i.e., hypertension) should be recorded on the Adverse Event eCRF.

Observations of the same clinically significant vital sign abnormality from visit to visit should not be repeatedly recorded on the Adverse Event eCRF, unless the etiology

changes. The initial severity of the event should be recorded, and the severity or seriousness should be updated any time the event worsens.

### **5.3.5.6      Abnormal Liver Function Tests**

The finding of an elevated ALT or AST ( $>3 \times \text{ULN}$ ) in combination with either an elevated total bilirubin ( $>2 \times \text{ULN}$ ) or clinical jaundice in the absence of cholestasis or other causes of hyperbilirubinemia is considered to be an indicator of severe liver injury. Therefore, investigators must report as an adverse event the occurrence of either of the following:

- Treatment-emergent ALT or AST  $>3 \times \text{ULN}$  in combination with total bilirubin  $>2 \times \text{ULN}$ .
- Treatment-emergent ALT or AST  $>3 \times \text{ULN}$  in combination with clinical jaundice.

### **5.3.5.7      Deaths**

All deaths that occur during the protocol-specified adverse event reporting period (see Section 5.3.1), regardless of relationship to study drug, must be recorded on the Adverse Event eCRF and immediately reported to the Sponsor (see Section 5.4).

Death should be considered an outcome and not a distinct event. The event or condition that caused or contributed to the fatal outcome should be recorded as the single medical concept on the Adverse Event eCRF. Generally, only one such event should be reported. The term “sudden death” should only be used for the occurrence of an abrupt and unexpected death due to presumed cardiac causes in a subject with or without preexisting heart disease, within 1 hour of the onset of acute symptoms or, in the case of an unwitnessed death, within 24 hours after the subject was last seen alive and stable. If the cause of death is unknown and cannot be ascertained at the time of reporting, “unexplained death” should be recorded on the Adverse Event eCRF. If the cause of death later becomes available (e.g., after autopsy), “unexplained death” should be replaced by the established cause of death.

### **5.3.5.8      Preexisting Medical Conditions**

A preexisting medical condition is one that is present at the Screening visit for this study. Such conditions should be recorded on the General Medical History and Baseline Conditions eCRF.

A preexisting medical condition should be recorded as an adverse event only if the frequency, severity, or character of the condition worsens during the study. When recording such events on the Adverse Event eCRF, it is important to convey the concept that the preexisting condition has changed by including applicable descriptors (e.g., “more frequent headaches”).

### **5.3.5.9 Hospitalization or Prolonged Hospitalization**

Any adverse event that results in hospitalization or prolonged hospitalization should be documented and reported as a serious adverse event (per the definition of serious adverse event in Section 5.1.2), except as outlined below.

The following hospitalization scenarios are not considered to be serious adverse events:

- Planned in-clinic stay required by the protocol for the SAD and MAD parts of the study.

### **5.3.5.10 Overdoses**

Study drug overdose is the accidental or intentional use of the drug in an amount higher than the dose being studied. An overdose or incorrect administration of study drug is not an adverse event unless it results in untoward medical effects.

Any study drug overdose or incorrect administration of study drug should be noted on the Study Drug Administration eCRF.

All adverse events associated with an overdose or incorrect administration of study drug should be recorded on the Adverse Event eCRF. If the associated adverse event fulfills serious criteria, the event should be reported to the Sponsor immediately (i.e., no more than 24 hours after learning of the event; see Section 5.4).

## **5.4 IMMEDIATE REPORTING REQUIREMENTS FROM INVESTIGATOR TO SPONSOR**

Certain events require immediate reporting to allow the Sponsor to take appropriate measures to address potential new risks in a clinical trial. The Investigator must report such events to the Sponsor immediately; under no circumstances should reporting take place more than 24 hours after the Investigator learns of the event. The following is a list of events that the Investigator must report to the Sponsor within 24 hours after learning of the event, regardless of relationship to study drug:

- Serious adverse events.
- Non-serious adverse events of special interest.
- Pregnancies.

The Investigator must report new significant follow-up information for these events to the Sponsor immediately (i.e., no more than 24 hours after becoming aware of the information). New significant information includes the following:

- New signs or symptoms or a change in the diagnosis.
- Significant new diagnostic test results.
- Change in causality based on new information.
- Change in the event's outcome, including recovery.

- Additional narrative information on the clinical course of the event.

Investigators must also comply with local requirements for reporting serious adverse events to the local Health Authority and IRB/EC.

#### **5.4.1        Emergency Medical Contacts**

To ensure the safety of study subjects, access to the Medical monitors is available 24 hours a day 7 days a week. Medical monitors' contact details are listed in the "Protocol Administrative and Contact Information & List of Investigators".

#### **5.4.2        Reporting Requirements for Serious Adverse Events and Non-Serious Adverse Events of Special Interest**

##### **5.4.2.1      Events That Occur prior to Study Drug Initiation**

After informed consent has been obtained but prior to initiation of study drug, only serious adverse events caused by a protocol mandated intervention should be reported. The Serious Adverse Event/Adverse Event of Special Interest Reporting Form provided to investigators should be completed and submitted to the SAE Responsible immediately (i.e., no more than 24 hours after learning of the event).

##### **5.4.2.2      Events That Occur after Study Drug Initiation**

For reports of serious adverse events and non-serious adverse events of special interest (see Section 5.1.2 and Section 5.1.3) that occur after initiation of study drug, investigators should record all case details that can be gathered immediately (i.e., within 24 hours after learning of the event) on the appropriate Adverse Event of Special Interest/ Serious Adverse Event eCRF form and submit the report via the electronic data capture (EDC) system. A report will be generated and sent to the Sponsor's Safety Risk Management department.

In the case of electronic reporting, investigators should record all case details that can be gathered immediately (i.e., within 24 hours after learning of the event) on the appropriate Serious Adverse Event / Adverse Event of Special Interest eCRF form and submit the report via the electronic data capture (EDC) system. A report will be generated and sent to the Sponsor's Safety Risk Management department.

In the event that the EDC system is unavailable, the Serious Adverse Event/Adverse Event of Special Interest Reporting Form provided to investigators should be completed and submitted to the SAE Responsible immediately (i.e., no more than 24 hours after learning of the event).

Once the EDC system is available, all information will need to be entered and submitted via the EDC system.

### **5.4.3        Reporting Requirements for Pregnancies**

#### **5.4.3.1      Pregnancies in Female Healthy Volunteers**

A female healthy volunteer of childbearing potential will be instructed to immediately inform the Investigator if she becomes pregnant during the study, and until the end of the follow-up period of 28 days.

A Clinical Trial Pregnancy Reporting Form should be completed by the Investigator and submitted to the Sponsor within 24 hours after learning of the pregnancy. Pregnancy should not be recorded on the Adverse Event eCRF. The Investigator should discontinue study drug and counsel the subject, discussing the risks of the pregnancy and the possible effects on the fetus. Monitoring of the subject should continue until conclusion of the pregnancy.

#### **5.4.3.2      Pregnancies in Female Partners of Male Healthy Volunteer**

Male healthy volunteers will be instructed through the Informed Consent Form to immediately inform the Investigator if their partner becomes pregnant during the study or within 28 days after the last dose of study drug. A Clinical Trial Pregnancy Reporting Form should be completed by the Investigator and submitted to the Sponsor within 24 hours after learning of the pregnancy. Attempts should be made to collect and report details of the course and outcome of any pregnancy in the partner of a male healthy volunteer exposed to study drug. The pregnant partner will need to sign an Authorization for Use and Disclosure of Pregnancy Health Information to allow for follow-up on her pregnancy. Once the authorization has been signed, the Investigator will update the Clinical Trial Pregnancy Reporting Form with additional information on the course and outcome of the pregnancy. An Investigator who is contacted by the male healthy volunteer or his pregnant partner may provide information on the risks of the pregnancy and the possible effects on the fetus, to support an informed decision in cooperation with the treating physician and/or obstetrician.

#### **5.4.3.3      Abortions**

Any spontaneous abortion should be classified as a serious adverse event (as the Sponsor considers spontaneous abortions to be medically significant events), recorded on the Adverse Event eCRF, and reported to the Sponsor immediately (i.e., no more than 24 hours after learning of the event; see Section 5.4).

Any induced abortion due to maternal toxicity and/or embryo-fetal toxicity should also be classified as serious adverse event, recorded on the Adverse Event eCRF, and reported to the Sponsor immediately (i.e., no more than 24 hours after learning of the event; see Section 5.4)

Elective abortion not associated with toxicity (e.g., induced abortion for personal reasons) does not require expedited reporting but should be reported as outcome of pregnancy on the Clinical Trial Pregnancy Reporting Form.

#### **5.4.3.4 Congenital Anomalies/Birth Defects**

Any congenital anomaly/birth defect in a child born to a female subject or female partner of a male subject exposed to study drug should be classified as a serious adverse event, recorded on the Adverse Event eCRF, and reported to the Sponsor immediately (i.e., no more than 24 hours after learning of the event; see Section [5.4](#)).

### **5.5 FOLLOW-UP OF SUBJECTS AFTER ADVERSE EVENTS**

#### **5.5.1 Investigator Follow-Up**

The Investigator should follow each adverse event until the event has resolved to baseline grade or better, the event is assessed as stable by the Investigator, the subject is lost to follow-up, or the subject withdraws consent. Every effort should be made to follow all serious adverse events considered to be related to study drug or trial-related procedures until a final outcome can be reported.

During the study period, resolution of adverse events (with dates) should be documented on the Adverse Event eCRF and in the subject's medical record to facilitate source data verification. If, after follow-up, return to baseline status or stabilization cannot be established, an explanation should be recorded on the Adverse Event eCRF.

All pregnancies reported during the study should be followed until pregnancy outcome and reported according to the instructions provided in Section [5.4](#).

#### **5.5.2 Sponsor Follow-Up**

For serious adverse events, non-serious adverse events of special interest, and pregnancies, the Sponsor or a designee may follow up by telephone, fax, electronic mail, and/or a monitoring visit to obtain additional case details and outcome information (e.g., from hospital discharge summaries, consultant reports, autopsy reports) in order to perform an independent medical assessment of the reported case.

### **5.6 POST-STUDY ADVERSE EVENTS**

The Investigator is not required to actively monitor subjects for adverse events after the end of the adverse event reporting period (defined as 28 days after the last dose of study drug).

If the Investigator becomes aware of any other serious adverse event occurring after the end of the adverse event reporting period, if the event is believed to be related to prior study drug treatment the event should be reported directly to the Sponsor or its designee, either by faxing or by scanning and emailing the Serious Adverse Event Reporting Form using the fax number or email address provided to investigators.

## **5.7 EXPEDITED REPORTING TO HEALTH AUTHORITIES, INVESTIGATORS, INSTITUTIONAL REVIEW BOARDS, AND ETHICS COMMITTEES**

The Sponsor will promptly evaluate all serious adverse events and non-serious adverse events of special interest against cumulative product experience to identify and expeditiously communicate possible new safety findings to investigators, IRBs, ECs, and applicable Health Authorities based on applicable legislation.

To determine reporting requirements for single adverse event cases, the Sponsor will assess the expectedness of these events using the following reference document:

- [RO7020531 Investigator's Brochure](#)

The Sponsor will compare the severity of each event and the cumulative event frequency reported for the study with the severity and frequency reported in the applicable reference document.

Reporting requirements will also be based on the Investigator's assessment of causality and seriousness, with allowance for upgrading by the Sponsor as needed.

## **6. STATISTICAL CONSIDERATIONS AND ANALYSIS PLAN**

The analysis of complete data for the study will be performed when all healthy volunteers have either completed the follow-up period or have discontinued early from the study, all data from the study are in the database and have been cleaned and verified, and the database is locked.

### **6.1 DETERMINATION OF SAMPLE SIZE**

Four to six cohorts may be evaluated in the SAD part of the study (approximately 40-60 subjects in total), and *two to three* cohorts are anticipated for the MAD part of the study with approximately 20-30 subjects in total.

Ten healthy volunteers are planned to be enrolled at each dose level. They will be randomized to either active treatment (eight healthy volunteers per dose level) or placebo (two healthy volunteers per dose level). With eight healthy volunteers per dose group or cohorts, there is a 90% chance to observe at least one AE that has an incidence rate of 25% in the population.

### **6.2 SUMMARIES OF CONDUCT OF STUDY**

The number of healthy volunteers who are randomized, discontinue, or complete the study treatment and/or the entire study (including follow-up period) will be summarized by treatment. Reasons for premature study withdrawal during MAD treatment and follow-up phase will be listed and summarized by treatment. Enrollment and protocol deviations will be listed and evaluated for their potential impact on interpretation of study results. Descriptive statistics will be used to evaluate the conduct of the study.

## **6.3 ANALYSIS POPULATIONS**

### **6.3.1 Safety Analysis Population**

All healthy volunteers who have received at least one dose of the study medication, whether prematurely withdrawn from the study or not, will be included in the safety analysis.

### **6.3.2 Pharmacokinetic Analysis Population**

A per protocol analysis including all healthy volunteers randomized and adherent to the protocol will be performed. Healthy volunteers will be excluded from the pharmacokinetic analysis population if they significantly violate the inclusion or exclusion criteria, deviate significantly from the protocol or if data are unavailable or incomplete which may influence the pharmacokinetic analysis. Excluded cases will be documented together with the reason for exclusion. All decisions on exclusions from the analysis will be made prior to database closure.

### **6.3.3 Pharmacodynamic Analysis Population**

PD analysis population will include all subjects who were randomized, received at least one dose of study medication (RO7020531 or placebo), and have PD data available. Subjects will be analyzed according to the treatment group to which they are randomized.

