### **3.1 DESCRIPTION OF STUDY**

#### **3.1.1 Overview of Study Design**

For both SAD and MAD parts of the study, each cohort will enroll ten subjects, with eight subjects randomly assigned to RO7020531 and two subjects randomly assigned to placebo ([Table 1](#)). Each cohort will include a minimum of two females, with at least one female receiving active drug. All single and multiple doses will be administered in the fasted state.

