### **3.1.1.2      Multiple Ascending Dose Study**

The trigger to start the first cohort in the MAD includes documentation of adequate safety and tolerability in the SAD cohorts and evidence of PD effects. For a given dose evaluated in the SAD, evidence in at least two subjects exhibiting responses above placebo-defined baseline for select PD biomarkers, including *the protein and metabolite markers IFN- $\alpha$ , IP-10, TNF- $\alpha$ , IL-6, IL-10, IL-12p40 and neopterin and markers of transcriptional responses (ISG15, OAS-1, MX1 and TLR7)*, should be demonstrated. If the next dose in the SAD has been considered safe, then the previous dose demonstrating TLR-associated PD activity will be considered as the starting dose for the MAD. In addition, the starting dose/exposure in the MAD part of this study should have been considered safe in the global EIH study (NP39305). Only doses covered by the dose range evaluated in the SAD part will be used in the MAD, and two to three dose levels will be evaluated (Figure 1).

[figure not shown]
Once criteria have been reached to determine an initial dose for MAD, subjects will be screened up to 28 days before enrollment into the MAD part of this study. They will be asked to remain in the unit from Day -2 until Day 14 with QOD dosing initiated on Day 1. In total, 7 QOD doses will be administered with the last dose given on Day 13. Subjects will be discharged on Day 14. After completing 7 QOD doses, each subject in the MAD cohorts will return for an outpatient follow-up visit 7 days after the last dose. All subjects will have a follow-up phone call 28 days after their last dose. Subjects will be asked to report any AEs that occur during this period.

Upon safety review of the MAD cohort(s) data, dose escalation will proceed in the MAD part of this study. The maximum dose investigated in MAD will not exceed doses

evaluated in the SAD part of this study nor will it exceed doses and exposures considered to be safe and with acceptable tolerability in the global EIH study.

Based on the PK, PD and safety evaluation of the previous dose cohorts, additional cohorts of subjects may be enrolled at higher or lower dose levels, or at a dose level already tested.

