#### **4.3 METHOD OF TREATMENT ASSIGNMENT AND BLINDING**

This study is observer-blinded. This means that the subjects, the Investigator, and all individuals in direct contact with the subjects at the investigative site will be blinded, except for the pharmacy staff handling the study drug distribution.

This study is Sponsor-open; members of the Sponsor's project and study teams who do not have direct contact with the subjects will be unblinded. This may exclude contract research organization (CRO) staff in direct contact with the site.

Healthy volunteers will be randomized 4:1 to RO7020531 or to placebo in each dose cohort. The randomization numbers will be generated by the Sponsor or its designee. The randomized treatment assignment will be allocated from the list sequentially to subjects in the order in which they are randomized. A minimum of two females per cohort will be randomized, with at least one female receiving active drug. The treatment allocation will be managed by the unblinded site pharmacist(s) and will be based on the randomization code list.

To allow informed recommendations or decisions regarding the dose decisions in this study, an integrated assessment of the available data on PK, select PD, safety and tolerability will be made prior to each dose decision.

In exceptional cases, (e.g., if deemed important for dose decisions or for the more thorough evaluation of safety-related concerns that may impact dosing of future subjects on this or other currently conducted or shortly to start studies involving administration of RO7020531) and in the interest of the subjects' safety, the Investigator may be unblinded after approval by the Clinical Pharmacologist.

The Principal Investigator(s) will receive a set of sealed treatment codes. These may have the form of sealed envelopes or scratch codes. If the identity of the test medication needs to be known in order to manage the healthy volunteer's condition, the treatment code for that healthy volunteer may be broken.

As per Health Authority reporting requirements, the Sponsor will break the treatment code for all unexpected serious adverse events (see Section 5.1) that are considered by the Investigator to be related to study drug.

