### **4.4.2 Dosage, Administration and Compliance**

#### **4.4.2.1 RO7020531 and Placebo**

Both RO7020531 and placebo will be administered orally in capsules.

In the SAD cohorts, RO7020531 or matching-placebo will be administered orally to the subjects by investigational staff on the morning of Day 1 after an overnight fast of at least 10 hours. Subjects in the SAD cohorts will not eat for 4 hours after the dose is administered. Water will be allowed ad libitum until one hour prior to dosing and after one hour post-dosing. Approximately 4 hours after dosing, subjects will be given lunch. The SAD part of the study will include an adaptive number of cohorts (approximately four). Each dose cohort will include 10 subjects (eight active and two placebo). *The planned dose-escalation sequence for SAD is shown in Table 1.*

*Doses of RO7020531 in SAD and MAD cohorts will be administered as a combination of 10 mg or 100 mg capsules with the requisite number of capsules being administered per specific dose cohort. Should an intermediate dose be required due to a change in the*

anticipated dose-escalation, the dose will be composed of the appropriate combination of 10 mg and 100 mg capsules.

In the MAD cohorts, RO7020531 or matching-placebo will be administered orally to the subjects by investigational staff QOD from Day 1 through to Day 13. In total, seven doses will be given (for time-points see [Appendix 3](#) and [Appendix 4](#)). Each dose will be given in a fasted state (after an overnight fast of at least 10 hours). Subjects will not eat for 4 hours after each dose is administered. Water will be allowed ad libitum until one hour prior to dosing and after one hour post-dosing. The MAD part of the study will include an adaptive number of cohorts (two to three). Each dose cohort will include ten subjects (eight active and two placebo). Dose levels for MAD will be defined during the study conduct based on emerging data (See [Table 1](#)).

Doses will be given orally with 240 mL of water. Additional amounts of water up to 100 mL could be given to assist dose administration only if needed.

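### Section 6.3.3 groups PD data by randomised rather than received treatment, so a recorded dispensing error would stay mislabelled in the final PD tables.

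*Combined protocol and SAP*

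**What the plan says.** Section 6.3.3 admits to the PD population every randomised subject who "received at least one dose of study medication (RO7020531 or placebo), and have PD data available". It then fixes the grouping: "Subjects will be analyzed according to the treatment group to which they are randomized". No as-received rule or sensitivity analysis for PD appears anywhere in the plan.

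The surrounding sections are these:

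- **Purpose of the PD data.** Section 2.2 sets a secondary objective on the effect of RO7020531 on PD parameters. Section 6.7 summarises PD descriptively by arm and explores how dosing regimen, PK and PD are related.
- **Group sizes.** Section 3.1.1 gives each cohort "eight subjects randomly assigned to RO7020531 and two subjects randomly assigned to placebo".
- **Recording of errors.** Section 5.3.5.10 requires incorrect administration to be noted on the drug administration eCRF page. Section 6.2 has protocol deviations listed and assessed for their influence on interpretation. Neither section moves a misdosed subject to another group.
- **Neighbouring populations.** The PK population (6.3.2) is per protocol and can exclude significant deviators, with reasons documented. The safety population (6.3.1) states no grouping rule.

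**The concern.** Grouping as randomised protects a randomised comparison of efficacy. The PD analysis here makes no such comparison: it has no formal test and asks how dose and exposure relate to biological response. For that question, a volunteer who swallowed active drug carries information about active drug, whatever the randomisation list says.

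Under the written rule such a volunteer would be tabulated as placebo if randomised to placebo, and a placebo recipient randomised to active would be averaged into a dose group. The study team would know what was taken, but the analysis rule would disregard it. Correcting the grouping later would depart from the plan, after the data had been seen, in a study where the sponsor's team is unblinded (Section 4.3). What is at stake is how faithfully the final descriptive PD tables reflect dose, most of all for the small placebo group.

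**Working it through.** **The plan's own figure.** The only sample-size figure, in Section 6.1, is a 90% chance of seeing at least one adverse event of 25% incidence in eight subjects. It reproduces: 1 − 0.75^8 = 0.8999. It concerns safety, and no PD power or error rate exists for the grouping rule to alter.

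**Inputs.**
- Active subjects per cohort: 8; placebo: 2 (Section 3.1.1, Table 1; the 4:1 ratio in Section 4.3 agrees).
- Single-dose cohorts: "Four to six cohorts may be evaluated in the SAD part of the study" (Section 6.1), but Section 3.1.1.1 allows stopping at three. Pooled placebo is then 3 × 2 = 6 to 6 × 2 = 12.
- Multiple-dose cohorts: two to three (Section 4.4.2.1). Pooled placebo is 4 to 6.
- Dispensing-error rate: not given. Everything below is conditional on exactly one error.

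**Share of a group that is mislabelled** = 1/n.

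| Group as randomised | n | Share |
|---|---|---|
| One dose group | 8 | 1/8 = 12.5% |
| One cohort's placebo | 2 | 1/2 = 50% |
| Single-dose placebo, pooled | 6 to 12 | 1/6 = 16.7% to 1/12 = 8.3% |
| Multiple-dose placebo, pooled | 4 to 6 | 1/4 = 25% to 1/6 = 16.7% |

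**Effect on the mean contrast.** Assume active drug shifts the PD measure by a constant amount. The share of the true active-minus-placebo difference that the table would show is:

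- Active given to a placebo-randomised subject: 1 − 1/n_placebo. This is 50% against the cohort's own placebo, and 83.3% to 91.7% against pooled single-dose placebo.
- Placebo given to an active-randomised subject: 1 − 1/8 = 87.5%.
- Two subjects swapped within a cohort: 1 − 1/n_placebo − 1/8. This is 37.5% against the cohort's own placebo, and 70.8% (n = 6) to 79.2% (n = 12) against pooled single-dose placebo.

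**After the change.** Grouping by treatment received leaves no mislabelled subject, so under the same assumption the expected contrast is retained in full. It does not restore a lost comparator: if one placebo-randomised subject takes active drug, that cohort has 8 + 1 = 9 active and 2 − 1 = 1 placebo subjects.

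**The case against.** The rule is explicit, specified in advance and contradicted by no other section. The harm is hypothetical: unblinded pharmacy staff dispense from the code list (4.3), a designated person prepares each dose to the schedule and documents it (4.4.2.1), and nothing suggests that an error is likely. PD is secondary and descriptive. An error would be visible through the eCRF and the deviation listing, and analyses of PD against measured concentration do not depend on the arm label. All of this stands and keeps the point minor. It does not make as-randomised grouping suit the question, and recording an error does not regroup the subject.

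Three stronger readings are tempting, and the documents do not support them.

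- *The rule could hide responders when the multiple-dose part is triggered.* Section 3.1.1.2 asks for "evidence in at least two subjects exhibiting responses above placebo-defined baseline for select PD biomarkers", so a contaminated placebo group looks dangerous. But Section 6 describes analysis of complete data after database lock, and 6.9 plans no interim analysis. The start decision comes from a continuing sponsor-open review of PK, PD and safety (3.1.1.1, 4.3), and nothing says that 6.3.3 governs it.
- *Combining capsule strengths makes a swap likely.* Section 4.4.2.1 says of an intermediate dose that "the dose will be composed of the appropriate combination of 10 mg and 100 mg capsules". A miscount would give a wrong amount of active drug. It is not evidence for an active/placebo exchange, which is the error quantified here.
- *PK and PD tables would contradict each other on dose.* The two populations differ by design. Leaving a misdosed volunteer out of PK is a documented exclusion, not a conflicting dose label.

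**Conclusion.** The point holds as a minor, no-cost improvement to Section 6.3.3, limited to the final PD tables. Its effect is zero if no dispensing error occurs. If one does, the mislabelled share is 12.5% of a dose group, 50% of a cohort's placebo group, or about 8% to 17% of pooled single-dose placebo. The 50% figure applies only if placebo is summarised by cohort, and the plan leaves that open. The contrast figures rest further on a constant response shift.

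A reader might infer a threat to dose selection or to the study's conclusions. The documents establish neither, and no stated sample size, power or error rate changes. The silence of Section 6.3.1 on grouping is missing detail, not a second error.

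**What to change.** In Section 6.3.3, replace the grouping sentence so that PD data are analysed according to the treatment and dose actually received. Have the deviation listing already planned in Section 6.2 identify any subject whose received and randomised treatment differ. Stating the same rule in Section 6.3.1 would be a useful but optional clarification.

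The cost is one sentence. The drug administration eCRF page already records incorrect administration, so no new data are needed. Sample size, procedures and dosing are untouched, and with no formal PD test nothing is lost by giving up as-randomised grouping.
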